5.2 Primary Endpoint

Overall duration of follow-up care and incidence of secondary surgical interventions will be analyzed to evaluate overall effectiveness of the use of the coflex® Interlaminar Technology

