Study Design	Retrospective, multi-center, post-market clinical study
Devices	coflex® Interlaminar Technology
Data Collection	Clinical, radiologic and patient reported outcomes data will be collected for approximately 5000 patients from 50 sites
Study Duration	Up to 6 months for data collection Start Date: June 2013 End Date: April 2017
Study Objectives	
Primary Objective:
 
• To assess the operative details and safety outcomes associated with the use of the coflex device• To assess post-operative adverse events• To assess post-operative follow-up duration 
Secondary Objectives:
 
• To measure and compare patient reported outcomes (e.g., VAS, Patient Satisfaction and ODI) at baseline and final follow-up• To measure and compare clinical and radiologic outcomes at baseline and final follow-up• To measure and compare the clinical, radiologic, and patient reported outcomes at interim follow-up visits• To assess the impact of demographics and risk factors on clinical, radiologic, and patient reported outcomes•
Inclusion Criteria	Patients must meet the criteria specified in the device labeling including radiographic confirmation of at least moderate lumbar stenosis, which narrows the central spinal canal at one or two contiguous levels from L1-L5 that require surgical decompression.
Exclusion Criteria	There are no exclusion criteria's for this study.

Risk/Benefit Assessment

The study is a retrospective analysis of medical records that poses no risk to the patients and minimal risk to loss of patient privacy. All results will be de-identified in the process of data review. There are no benefits to the subject as this data is being collected to obtain additional clinical evidence to support publications and marketing.

Study Abbreviations

Abbreviation	Definition
BMI	Body Mass Index
FDA	Food and Drug Administration
GCP	Good Clinical Practice
HIPAA	Health Insurance Portability and Accountability Act of 1996
ICH	International Committee on Harmonization
IRB	Institutional Review Board
MRI	Magnetic Resonance Imaging
CT	Computed Tomography
DEXA	Dual Energy X-ray Absorptiometry

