2.0 Study Purpose

2.1 Primary Objective

- To assess the operative details and safety outcomes associated with the use of the coflex device
- To assess post-operative adverse events
- To assess post-operative follow-up duration

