4.0 Study Design

This is a retrospective, multi-center, post-market study collecting clinical, radiographic, and patient reported outcomes for subjects who have been treated 1 or 2 levels with the coflex® Interlaminar Technology or decompression with or without fusion.

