4.4.2 Surgical Treatment Visit

- Operative Summary
 - Date of surgery
 - Surgical procedure
 - Operative time
 - Estimated blood loss
 - Anesthesia details
 - Treated level(s)
 - Device size
 - Intra-operative/early post-operative complications, such as:
 - Dural tears
 - Hematomas
 - Fractures
 - Nerve injury
 - Diagnostic imaging History
 - Dictated operative notes
- Repeat Surgery Summary
 - Date of surgery
 - Reason for surgery (reoperation, revision, removal, etc.)
 - Surgical procedure
 - Operative time
 - Estimated blood loss
 - Anesthesia details
 - Treated level(s)
 - Surgical intervention performed
 - Device size
 - Intra-operative/early post-operative complications

- Dural tears
- Hematomas
- Fractures
- Nerve injury
- Diagnostic imaging History

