4.4.4 Follow-Up Visits

The following longitudinal data will be collected for all follow-up clinic visits through final follow-up:

- Work status / ADL
- Compliance with postoperative protocol/restrictions (if applicable)
- VAS (as available)
- ODI (as available)
- Patient satisfaction (as available)
- Complications
- Secondary treatments
- Narcotics use
- Diagnostic Imaging
- Incidence of Epidural Steroid Injections (ESI)

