5.0 Statistical Analysis

5.1 General Information

All continuous outcome measurements at follow-up time points will be compared to baseline values using a t-test for superiority. Categorical outcome measurements will be compared using a Fisher's exact test for superiority. Statistical significance for these analyses will be demonstrated with a p-value less than 0.05.

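### The primary endpoint counts secondary surgery with no time horizon, time at risk or censoring rule, and judges effectiveness by an undefined follow-up duration

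*Combined protocol and SAP*

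**What the plan says.** Section 5.2 is the whole specification of the primary endpoint: "Overall duration of follow-up care and incidence of secondary surgical interventions will be analyzed to evaluate overall effectiveness" of the coflex device.

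The surrounding sections add the following:

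- **Tests.** Section 5.1 names two, with significance at p below 0.05 and no statement of one- or two-sided testing. For continuous outcomes: "All continuous outcome measurements at follow-up time points will be compared to baseline values using a t-test for superiority". For categorical outcomes: "Categorical outcome measurements will be compared using a Fisher's exact test for superiority".
- **Follow-up.** Section 4.4.4 says that "longitudinal data will be collected for all follow-up clinic visits through final follow-up". Final follow-up is not defined, and the table in section 4.2 has a single follow-up column with no months or windows.
- **Objective.** Section 2.1 lists, among the primary objectives, "To assess post-operative follow-up duration", without saying what is measured or which direction is good.
- **Population.** Section 4.0 takes in patients "who have been treated 1 or 2 levels with the coflex® Interlaminar Technology or decompression with or without fusion", and the title sets coflex versus decompression.
- **Dates.** Section 4.4.2 collects the dates of index and repeat surgery and the reason for the repeat. Section 4.4.1 lists a visit date at baseline; section 4.4.4 lists none at follow-up.

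**The concern.** The incidence of reoperation has meaning only together with the time over which patients were watched. These charts can run for very different lengths, and the plan neither fixes a time point nor uses person-time. Fisher's test treats a patient seen for six months without reoperation the same as one seen for three years.

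Section 5.2 does not spell out a between-group comparison, but the title and the comparator patients imply one. If it is made with Fisher's test, a difference in follow-up alone can create or hide a difference in reoperation. If only coflex patients are analysed, the proportion still changes with chart length.

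The second component has its own problem. Duration of follow-up care could mean how long patients needed care, or how long they happened to be observed. Long follow-up could mean persistent trouble or good retention. It has no baseline value, so the one continuous test in section 5.1 does not fit it.

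This is the primary endpoint and the stated basis for effectiveness.

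**Working it through.** **Inputs from the documents.** Significance level 0.05 (5.1). About 5000 patients from 50 sites, with no split by treatment (Protocol Summary). Study dates: "Up to 6 months for data collection Start Date: June 2013 End Date: April 2017"; June 2013 to April 2017 is 46 months, but the plan does not say that these dates bound the surgeries. It states no event rate, effect size or power, so there is no figure of its own to reproduce.

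**Assumptions, for illustration only.** Reoperation hazard of 5% per year unless stated; mean follow-up of 18 to 24 months; groups of 500, 1000 and 2500 (the last is an even split of 5000); two-sided tests; censoring independent of outcome; 4000 simulated datasets per scenario.

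**Step 1: crude incidence.** With fixed follow-up, incidence = 1 − exp(−cumulative hazard).

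- 12 months: 1 − exp(−0.05) = 4.9%
- 18 months: 1 − exp(−0.075) = 7.2%
- 22 months: 1 − exp(−0.0917) = 8.8%
- 24 months: 1 − exp(−0.10) = 9.5%

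So for coflex alone, one and the same hazard reads as 4.9%, 7.2% or 9.5% according to whether charts run 12, 18 or 24 months.

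**Step 2: false rejection when the groups do not differ.**

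| Scenario, same hazard in both groups | Crude incidence | Fisher rejects, n = 500 / 1000 / 2500 per group |
|---|---|---|
| (a) 18 vs 24 months for all | 7.2% vs 9.5% | 22.7 / 42.8 / 82.7% |
| (b) Exponential follow-up, nominal means 18 vs 24, capped at 46 months (realised 16.6 vs 20.5) | 6.5% vs 8.0% | 12.1 / 21.8 / 48.1% |
| (c) 5%/year in year 1, then 1.5%/year; 18 vs 24 months | 5.6% vs 6.3% | 6.3 / 7.7 / 16.1% |
| (d) 22 vs 24 months | 8.8% vs 9.5% | 5.5 / 7.7 / 14.1% |
| (e) 24 vs 24 months | 9.5% vs 9.5% | 4.1 / 4.5 / 4.0% |

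For (c), the cumulative hazards are 0.05 + 0.0075 = 0.0575 and 0.05 + 0.015 = 0.065. A log-rank test on the same datasets rejects in 4.5 to 5.5% throughout.

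**Step 3: a true effect hidden.** Take 5% per year over 18 months against 3.75% per year over 24 months (hazard ratio 0.75). The cumulative hazards are 0.05 × 1.5 = 0.075 and 0.0375 × 2 = 0.075, so both groups show 7.2%. Fisher rejects in 4.0 / 3.8 / 4.4%; log-rank in 18.4 / 37.0 / 72.5%.

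**Step 4: the crude table cannot tell the explanations apart.** A hazard ratio of 0.75 with 24 months in both groups gives 7.2% against 9.5%. That is the same pair as scenario (a), where there is no effect at all.

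**Step 5: other hazards and splits.** For fixed follow-up of 18 vs 24 months at 2500 per group, a normal approximation gives 47% false rejection at 2% per year, 75% at 4% and 89% at 6%. A 4000:1000 split at 4% gives 58%. In a separate simulation of 2000 runs at 4% per year, with follow-up as in (b) and 2500 per group, Fisher rejected in 40%. A person-time rate-ratio test stayed between about 4% and 6% in every setting tried.

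**Step 6: the duration component.** Sections 2.1, 5.1 and 5.2 together give no start or end point, no favourable direction and no test that fits. If it means length of observation, it is also the exposure time for the other component: at equal hazard, the group watched for less time shows fewer reoperations.

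**The case against.** The strongest reply is that section 5.2 speaks only of coflex and states no between-group test of reoperation, so the false-rejection figures belong to an analysis that the plan does not write down. That is fair. The comparison is inferred from the title and from sections 4.0 and 4.2, and the figures are conditional on it.

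Nor does any section give a reason to expect follow-up to differ by treatment. Variation between patients is not variation between groups, and scenario (e) shows no inflation when follow-up matches. The large figures need a sizeable gap and large groups.

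The hidden-effect example is a constructed balance. With the same hazards and 24 months in both groups, Fisher rejects in about 22%, 44% and 82%. With the gap reversed, it rejects in about 64%, 92% and over 99%. The example shows what can happen, not what is likely.

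For coflex alone, duration is reported beside incidence, so a reader could form a rough rate. The plan does not say to do so, and a rate built from totals assumes a constant hazard. Section 5.1 is better described as silent on duration than as misapplying a test to it.

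Finally, the log-rank test holds its level here because censoring was simulated as independent. In charts, patients who do well may stop attending. Survival methods remove the dependence on unequal chart length, but not informative loss.

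None of this supplies the missing horizon, denominator or censoring rule.

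**Conclusion.** The concern holds and should be fixed before analysis. The defect is one of specification and does not rest on any assumed hazard: the primary endpoint has no horizon, time at risk or censoring rule, and its duration component has no definition or direction. Following the plan as written gives a crude proportion mixed with chart length.

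How much this matters depends on unknowns. If a between-group Fisher test is used, false rejection ranges from no inflation with equal follow-up, through 6 to 16% with a front-loaded hazard or a two-month gap, to 23 to 83% with a constant 5% per year hazard and a six-month gap. These ranges assume two-sided testing, independent censoring and 500 to 2500 patients per group.

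**What to change.** - **Reoperation.** Define the endpoint as time from index surgery to first secondary surgical intervention, censored at last chart contact. Report Kaplan-Meier estimates with 95% confidence intervals at fixed times, for example 12 and 24 months, by treatment.
- **Comparison.** State whether a between-group comparison is planned. If so, use a Cox model adjusted for named baseline covariates, and check proportional hazards.
- **Censoring.** State the non-informative-censoring assumption and that it may fail in chart data. Treat death as a competing event only where the chart records it.
- **Duration.** Define its start and end, report it descriptively by group, and do not use it as evidence of effectiveness. This still meets the objective in section 2.1.

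**Cost.** Rewording of section 5 and standard survival code. Surgery and repeat-surgery dates are already collected under section 4.4.2. A last-contact date must be added for every patient before chart abstraction closes, although assessing follow-up duration needs one in any case. Two downsides remain: one named primary measure becomes descriptive, and death is not a listed data item, so competing-risk handling will be incomplete.

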5.3 Secondary Endpoints

The clinical outcomes will be summarized; however, since the collection of these measures is not standard of care, this data will only be collected as available. In addition, data will be used to analyze the association between coflex® Interlaminar Technology use and outcomes with age, ethnicity, race, workers' compensation, smoking status, and gender. New and/or worsening complications will be summarized.

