2.2 Secondary Objectives

The secondary objectives of this study are:

- To measure and compare patient reported outcomes (e.g., VAS, Patient Satisfaction and ODI) at baseline and final follow-up
- To measure and compare clinical and radiologic outcomes at baseline and final follow-up
- To measure and compare the clinical, radiologic, and patient reported outcomes at interim follow-up visits
- To assess the impact of demographics and risk factors on clinical, radiologic, and patient reported outcomes

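### Section 5.3 asks how outcomes relate to coflex use and six patient factors, but the tests in section 5.1 cannot show whether change differs by factor, test an interaction, or separate correlated factors

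*Combined protocol and SAP*

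**What the plan says.** Section 2.2 lists as a secondary objective "To assess the impact of demographics and risk factors on clinical, radiologic, and patient reported outcomes". Section 5.3 turns this into an analysis: the data will be used to "analyze the association between coflex® Interlaminar Technology use and outcomes with age, ethnicity, race, workers' compensation, smoking status, and gender". It names no method.

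The inferential methods are all in section 5.1. For continuous outcomes, "All continuous outcome measurements at follow-up time points will be compared to baseline values using a t-test for superiority". For categorical outcomes, "Categorical outcome measurements will be compared using a Fisher's exact test for superiority", without naming the groups compared. The threshold is common to both: "Statistical significance for these analyses will be demonstrated with a p-value less than 0.05".

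The setting matters too. Section 4.0 describes a retrospective study of patients "treated 1 or 2 levels with the coflex® Interlaminar Technology or decompression with or without fusion", so treatment is not randomised. The Protocol Summary says that "data will be collected for approximately 5000 patients from 50 sites", with no split by procedure. Section 5.3 adds, for the clinical outcomes, that "this data will only be collected as available", so the number with usable data may be well below 5000.

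No regression, interaction term, covariate adjustment, stratified analysis, rule for coding age or multiplicity rule appears in the document.

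**The concern.** The question in section 5.3 involves a procedure, an outcome and six factors at once. Neither listed test can handle that structure.

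- **t-test against baseline.** Within any group it asks whether the mean changed after surgery. Run separately in smokers and non-smokers, it can say that both improved. It does not compare the two improvements.
- **Fisher's exact test.** It can compare a categorical outcome across the categories of one factor, or between procedures. It cannot take age as a number, cannot test whether the procedure difference varies with a factor, and cannot hold one factor fixed while examining another.

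Two errors become possible. A factor may be credited with an effect that belongs to a correlated factor, for instance workers' compensation with that of smoking. And a statement about who benefits may rest on tests that do not address it, either by missing a real difference or by reading one into unequal subgroup sizes. The Risk/Benefit Assessment and section 1.0 say the data will support publications and marketing, so statements about patient types are a foreseeable use.

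**Working it through.** The plan gives no power, effect size, standard deviation (SD), event rate or allocation, so it has no figure of its own to reproduce. From the documents come the total of 5000, the six factors and the 0.05 threshold. All else below is assumed: two-sided testing, 1:1 procedures, effect sizes, subgroup shares and the correlation between factors. Φ is the standard normal distribution function.

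**1. Pre-post t-test when change really differs.** Assume a change of 0.7 SD in the smaller subgroup and 1.0 SD in the larger. Power within a subgroup of size n is Φ(d√n − 1.96). The least favourable case is 1000 analysable patients with a 5% subgroup (n = 50): Φ(0.7√50 − 1.96) = Φ(2.99) = 99.86%, and practically 100% in the other 950. Both subgroups are significant almost always, and the difference goes unseen. A direct test of the difference has power Φ(0.3/√(1/n₁ + 1/n₂) − 1.96):
- 1000 patients (50 and 950): Φ(2.07 − 1.96) = 54%
- 5000 patients (250 and 4750): Φ(4.62 − 1.96) = 99.6%

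**2. Subgroup p-values for the procedure comparison, with no effect modification.** Assume the same standardised procedure difference d in both subgroups. With m patients per arm, power is about Φ(d√(m/2) − 1.96). With powers p₁ and p₂, one subgroup is significant and the other not with probability p₁(1 − p₂) + p₂(1 − p₁).

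| Patients | Smaller subgroup | d | Power, smaller | Power, larger | Discordant |
|---|---|---|---|---|---|
| 5000 | 50% | 0.2 | 99.9% | 99.9% | 0.2% |
| 5000 | 20% | 0.2 | 88.5% | 100% | 12% |
| 5000 | 10% | 0.2 | 60.9% | 100% | 39% |
| 5000 | 5% | 0.2 | 35.2% | 100% | 65% |
| 5000 | 5% | 0.1 | 12.1% | 93.1% | 83% |
| 1000 | 20% | 0.2 | 29.3% | 80.7% | 63% |

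At d = 0.3 with an equal split of 5000 the figure rounds to zero.

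Fisher's test on repeat surgery behaves in the same way. Assume 10% versus 7% in every subgroup. Simulated power is 92.5% at 2000 per group, 22.5% at 300 and 10.1% at 150. Then significant in the large subgroup but not in the small one has probability 0.925 × (1 − 0.225) = 72% or 0.925 × (1 − 0.101) = 83%. Other assumed rates with the 2000 and 300 split give about 39% (10% versus 5%) and 16% (12% versus 5%, or 10% versus 9%). With equal subgroups of 1250 per arm and 10% versus 5%, discordance is under 1%.

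**3. Correlated factors.** Assume workers' compensation in 10% of patients with no effect, smoking in 40% of those and 20% of the rest, and a smoking effect of −0.3 SD. The unadjusted compensation contrast is then biased by −0.3 × (0.40 − 0.20) = −0.06 SD. Rejection rates over 1000 simulated studies:

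| Patients | Unadjusted | Adjusted for smoking |
|---|---|---|
| 5000 | 22.3% | 3.6% |
| 1000 | 10.1% | 5.3% |

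The nominal rate is 5%, and the adjusted figures lie within or near simulation error of it. As a check, the standard error at 5000 is about 0.0476, so z = 0.06/0.0476 = 1.26 and the closed-form rejection rate is about 24%. At 1000 it is about 9%.

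**4. Six factors at 0.05 each.** If the tests are independent and no factor has an effect, the chance of at least one significant result is 1 − 0.95⁶ = 26.5% per outcome.

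**The case against.** A reader might infer that the plan will judge effect modification by setting a significant subgroup beside a non-significant one. The documents do not say so. Section 5.3 mentions no subgroup, no test within a subgroup and no comparison of p-values. That route is one possible misuse of an analysis left without a method.

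Three further points stand.

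- Only the t-test is tied to baseline. Fisher's test could compare, say, repeat surgery directly between smokers and non-smokers. That is a legitimate test of one factor, though unadjusted.
- The sentence in section 5.3 may mean plain association between factors and outcomes. The objective in section 2.2 reads that way, and on that reading no interaction is needed.
- For pain and disability scores, a pre-post test will tend to be significant in every subgroup. The main risk there is a missed difference, not a false claim that the device works in one group and not in another.

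The discordance figures also depend heavily on assumptions, and with large balanced subgroups they can be negligible. None of this supplies a method that separates correlated factors, which either reading of section 5.3 needs in a non-randomised chart review.

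**Conclusion.** The point holds in a limited form. The tests in section 5.1 cannot show whether change in a continuous outcome differs by factor, cannot test a procedure-by-factor interaction, and cannot separate correlated factors. The plan therefore has no valid route to effect modification, and for plain association it has at most unadjusted comparisons.

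The size cannot be fixed from the documents. The firmest illustration is confounding between factors: false rejection in roughly 10% to 22% of studies, against about 5% when adjusted, given the assumed prevalences and smoking effect. If subgroup p-values were compared, the misleading pattern could be almost absent or could reach 83%; the upper figures should not be quoted alone.

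This is a secondary objective in a retrospective review, and better wording largely cures it. It is a cheap improvement.

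**What to change.** In section 5.3, first state the target: factor-outcome association, effect modification by procedure, or both. Then replace the section 5.1 tests for this analysis with one prespecified multivariable model per outcome:

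- linear regression for ODI and VAS, with the baseline score as covariate;
- logistic regression for secondary surgery and complications, or Cox regression where follow-up time is recorded;
- procedure and all six factors in the model together, age continuous, with allowance for site.

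If effect modification is a target, judge it only by the procedure-by-factor interactions with 95% intervals, and label these exploratory. Give subgroup estimates without subgroup p-values.

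Two data items need confirming. Workers' compensation is not named in the section 4.4 lists, although the section 4.2 table includes payer information. Section 4.4.4 names no follow-up visit date, although the follow-up duration in section 5.2 implies that one is available.

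The cost is analysis-plan wording and modest programming. Interaction estimates will be less precise, so fewer subgroup claims will be possible. Patients without a baseline questionnaire drop out of the ODI and VAS models unless missing values are handled, so the plan should say how.

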4.1 Endpoints

Patient reported outcomes will be assessed as part of the primary objective.

Clinical and radiologic outcomes, demographics and risk factors will be assessed as part of the secondary objectives. These include, but are not limited to:

- Age
- Gender
- Ethnicity
- Height and Weight
- BMI
- Narcotics use
- Comorbidities
- Bone Density
- Presenting Symptoms
- Radiologic Data (Anterior/Posterior and Flexion/Extension films, as well as, MRI and/or CT Scan used to confirm diagnosis of spinal stenosis)
- Operative Data
- Intra-Operative Complications
- Return to Work
- Changes in Activities of Daily Living (ADL)
- Patient Satisfaction
- Repeat Surgery Details

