4.2 Data Collection Summary

Subjects will have undergone a decompression surgery with the coflex® Interlaminar Technology, 1 or 2 level decompression with or without fusion according to the physician's standard procedures. Table 1 describes the anticipated time points which will be collected as part of the retrospective data review. Please see Section 4.4, Data Collection Procedures for additional details regarding the data points intended to be captured at the designated time points.

	Baseline	Surgical Treatment	Post-Operative Hospital Stay	Follow-Up Visit(s)
Demographics & Risk Factors	X			
Prior Surgery Detail (If available)	X			
Diagnosis	X			
Operative Summary		X		
Procedure Payer Information		X		
Secondary Treatments			X	X
Complications		X	X	X
Work Status / ADL (If available)	X		X	X
Patient Questionnaires (If available)	X	X	X	X
Diagnostic Imaging History	X	X	X	X

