4.4.1 Baseline Visit

- Diagnosis
 - Presenting symptoms
 - Documented failed conservative treatment
 - Patient reported outcome questionnaires, if available
 - Prior treatment details
- Pre-Operative Demographics
 - Date of visit
 - Age
 - Gender
 - Race
 - Ethnicity
 - Work Status / ADL
 - Height (in)
 - Weight (lbs)
 - BMI

- Risk Factors
 - Tobacco Use
 - Alcohol Use
 - Comorbidities
 - Diabetes
 - Bone Density
 - Medications
- Diagnostic Imaging
 - MRI and CT of affected lumbar levels
 - Radiographs

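### Section 5.3 only partly covers the objective on demographics and risk factors: smoking is the one listed risk factor it names, and number of levels and prior surgery enter no stated analysis

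*Combined protocol and SAP*

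**What the plan says.** Section 2.2 sets the objective: "To assess the impact of demographics and risk factors on clinical, radiologic, and patient reported outcomes". Section 4.1 supports it, stating that "Clinical and radiologic outcomes, demographics and risk factors will be assessed as part of the secondary objectives", and follows with a list described as non-exhaustive. That list includes BMI, narcotics use, comorbidities and bone density.

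Section 4.4.1 records tobacco use, alcohol use, comorbidities, diabetes, bone density and medications as risk factors. As demographics it records age, gender, race, ethnicity, work status/ADL, height, weight and BMI, besides the visit date. The table in Section 4.2 gives "Prior Surgery Detail" its own row, collected if available. Section 4.4.2 records the treated levels in the operative summary.

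The analysis sentence in Section 5.3 concerns the "association between coflex® Interlaminar Technology use and outcomes with age, ethnicity, race, workers' compensation, smoking status, and gender". Section 5.1 supplies the only methods: a t-test of follow-up against baseline for continuous outcomes and Fisher's exact test for categorical ones. It adds that "Statistical significance for these analyses will be demonstrated with a p-value less than 0.05".

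**The concern.** The analysis section is narrower than the objective it serves and narrower than the list in 4.1. An analyst who follows 5.3 as written reports on smoking and four demographics and says nothing about bone density, diabetes, other comorbidities, alcohol, medications or BMI. If these are added after the data have been seen, they are post hoc. That matters here because the sponsor collects and analyses the data itself (6.2) and intends them for publications and marketing (1.0).

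A second, separate issue is confounding. Patients received coflex or decompression with or without fusion according to each physician's usual practice, at one or two levels, and the study adds no exclusion criteria. Choice of procedure may therefore go with health status and extent of surgery. The factors that describe these are recorded, but no stated analysis adjusts for them.

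**Working it through.** The plan gives no figure to reproduce on this point. The check is an item-by-item comparison of what is recorded with what 5.3 names.

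**Coverage of the objective**

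| Recorded in 4.4.1 | Named in 5.3 | Not named in 5.3 |
|---|---|---|
| Risk factors (6) | tobacco, as smoking status (1) | alcohol, comorbidities, diabetes, bone density, medications (5) |
| Demographics (8, without visit date) | age, gender, race, ethnicity (4) | work status/ADL, height, weight, BMI (4) |

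- Together, 4 + 1 = 5 of 8 + 6 = 14 recorded items are named.
- The extracted text flattens list levels, so diabetes may be a sub-item of "Comorbidities". The risk-factor count would then be 1 of 5 and the total 5 of 13. The conclusion is the same.
- Height and weight are carried by BMI, so BMI is the material omission among the demographics.
- The sixth name in 5.3, workers' compensation, matches no explicit data item. The nearest are procedure payer information (4.2) and work status/ADL.
- Of the items listed in 4.1, BMI, comorbidities, bone density and narcotics use are absent from 5.3.

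**Method.** The t-test in 5.1 compares follow-up with baseline, so it does not relate an outcome to a patient factor. Fisher's test can cross a categorical outcome with one factor at a time. Neither holds one factor constant while examining another. So even the six named factors have no adjusted analysis.

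**Confounding: illustration on assumed inputs.** With no true treatment effect, the spurious difference between two groups is (difference in prevalence of the factor) × (difference in outcome between its levels).

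- Operative time, assuming 90 min for one level and 150 min for two, with 30% and 50% two-level cases: 0.7×90 + 0.3×150 = 108 min against 0.5×90 + 0.5×150 = 120 min, a difference of 12 min. A prevalence gap of 10 points instead of 20 gives 0.10×60 = 6 min. No gap gives 0.
- Repeat surgery, assuming 6% risk with normal and 12% with low bone density, at 20% and 40% prevalence: 0.8×6 + 0.2×12 = 7.2% against 0.6×6 + 0.4×12 = 8.4%, a difference of 1.2 points. A 10-point gap gives 0.6 points. No gap gives 0.

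None of these inputs is in the documents, and the sign could go either way. The figures show the mechanism only.

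**Feasibility of a larger model.** The plan expects "approximately 5000 patients from 50 sites". At an assumed repeat-surgery risk of 6% to 12%, 5000 patients give 300 to 600 events. With about 15 model terms that is 300/15 = 20 to 600/15 = 40 events per term, before any loss to missing covariates.

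**The case against.** The strongest reply is that 5.3 contains no restricting word, that 4.1 already promises assessment of risk factors through an open list, and that the variables are collected, so nothing prevents their analysis. This stands in part. A reader might infer that the objective cannot be met, or that 5.3 excludes the other factors. The documents support neither: four demographics and one risk factor are covered, and further factors are not barred. What remains is incomplete pre-specification. Section 4.1 gives no method, and 5.3 drops several of the items that 4.1 lists.

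A reader might also infer that leaving out number of levels and prior surgery breaches the objective. It does not. The protocol classes neither as a demographic or a risk factor: treated levels are operative data and prior surgery has its own row. They matter as adjustment variables.

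Nor can the 12 min or 1.2 points be read as bias in this study. Besides resting on assumed inputs, the operative-time example needs a between-procedure contrast that Section 5 does not specify for that outcome. Operative time has no baseline value, and the primary objective speaks of operative details with coflex. The device-labelling criteria may also narrow the variation between patients.

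Finally, the objective is secondary and the study is a chart review. That limits the severity. It does not remove the mismatch, which is cheap to repair before analysis.

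**Conclusion.** The point holds as a gap in pre-specification. Section 5.3 names 1 of 6 listed risk factors (1 of 5 if diabetes belongs under comorbidities) and 4 of 8 demographics. BMI, comorbidities and bone density are missing from it although 4.1 lists them. This rests on the text alone.

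The confounding point also holds, as a possibility. Treatment was not randomised, one- and two-level cases are mixed, and recorded health status, number of levels and prior surgery enter no stated adjustment. It assumes that 5.3 is meant to set coflex use against the other procedures, as the study title suggests. If only coflex patients were analysed, the factor associations would still be unadjusted for one another. The size cannot be derived from the documents.

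This should be changed before analysis, but it does not invalidate the study.

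**What to change.** - **Factor list.** Extend 5.3 to the recorded demographics and risk factors by adding BMI, alcohol use, diabetes, comorbidities, bone density and medications. Align it with 4.1 and 4.4.1.
- **Model.** Pre-specify one multivariable model per main outcome, containing procedure, these factors, number of treated levels, and prior surgery where available.
- **Missing data.** Report missingness for each factor and handle it by multiple imputation or a complete-case sensitivity analysis. A separate category for unrecorded values is not advised, because it can bias adjusted estimates.
- **Interpretation.** Label the risk-factor associations as exploratory, since many will be examined at the 0.05 level.
- **Operative data.** Report operative time, blood loss and hospital stay separately for one and two levels.
- **Workers' compensation.** State which collected item supplies it, for example payer information.

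The cost is a few lines in 5.3 and some additional analysis. The added factors are already collected; only the source of workers' compensation needs checking. The downsides are that some factors, such as bone density, will be incompletely recorded, and that more associations examined means more chance findings.
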